#### **4.2. Exclusion criteria:**

- History of prior CM
- Receipt of systemic antifungal medication for more than 4 consecutive weeks within the past 6 months
- Receipt of ART for more than 4 consecutive weeks within the past year
- For CrAg-positive patients only: Known to be currently pregnant or planning to become pregnant during the study period

### **Eligibility criteria for phase 2**

In Phase 1, patients were prescreened for eligibility *to enroll in the longitudinal study*, and CrAg testing was only performed on patients who met study eligibility criteria (as above) and for whom the clinician filled out a CrAg requisition form as part of the study.

Phase 2, has no longitudinal component, and CrAg screening will be implemented in a programmatic manner. The national guidelines recommend “screening for serum *Cryptococcus neoformans* antigen (CrAg) in adults who have not received ART with CD4 count below 100 cells/ $\mu$ L.” Thus, in phase 2, as per national guidelines, CrAg screening will be performed reflexively on all HIV positive ART Naïve and experienced adults with CD4<100 cells/ $\mu$ L or with WHO stage 3 or 4 who are enrolled for care at the CRICS OPCs or are receiving inpatient or outpatient care at a facility whose CD4 testing is conducted by one of the CRICS labs. CrAg screening will also be done if requested by providers based on CD4 or clinical criteria.

## 5. Study sites

### Phase 1

Eligible patients will be enrolled consecutively from 22 participating OPCs. See sites by region and number of patients starting ART in 2013, an indication of the volume of patients at each site. Program data are not disaggregated by CD4  $\leq$  or  $>100$  cells/ $\mu$ L; approximately 1/3 to ½ are expected to have CD4  $\leq$ 100 cells/ $\mu$ L [16]. The sites have been purposefully selected to represent: (1) district, provincial or national level; (2) facilities able to provide primary or tertiary care; (3) rural, peri-urban, and urban location; (4) facilities with a sufficient number of patients; and (5) different capacity for diagnostic investigations. For logistical reasons, only two sites will be recruited from the middle of Vietnam, a reflection of the relatively lower prevalence of HIV and lower number of PLHIV and treatment facilities in this region. The prevalence of cryptococcal disease in this region has not been previously assessed and findings from these sites will help to determine if another prevalence study will be required.

## **Phase 2: Types of study sites**

For purposes of this study and as described above we have characterized three potential types of sites:

(i) **CRICS sites**- This includes the 22 OPCs participating in Phase 1. Based on number of CrAg-positive patients identified at given OPCs, resources, and logistics, CrAg screening may not continue at all 22 Phase 1 sites during Phase 2.

(ii) **Inpatient wards affiliated with the 22 OPCs**- These wards are often co-located with the OPCs. Patients with  $CD4 \leq 100$  cells/ $\mu$ L or with WHO stage 3 or 4 will be screened for CrAg at the discretion of their providers. Patients with symptoms of meningitis will be tested for diagnostic purposes (blood and/or CSF) regardless of CD4 count.

(iii) **Expanded OPCs**- Reflex CrAg screening will be expanded to additional OPCs (preferentially to OPCs whose CD4 testing is conducted at laboratories already conducting CrAg screening as part of Phase 1).

Participation of sites and patients might not be consistent during Phase 2:

- Because of transition of finances from international donors to Vietnamese sources and from CD4 to viral load monitoring, CD4 testing may be unstable:
  - Participating laboratories might temporarily run out of reagents
  - If CD4 machines break down, resources might or might not be available to repair them
  - Some laboratories might cease CD4 testing altogether

When this happens, if a different laboratory assumes CD4 testing for a given OPC, CrAg screening at those OPCs might not continue if that laboratory has not been conducting CrAg screening. In these cases, CrAg screening will be performed when requested by the primary provider for those with WHO stage 3 or 4 or those with overt symptoms of meningitis.

- If a given laboratory assumes CD4 testing for multiple other laboratories, the burden of CD4 testing might preclude CrAg testing.
- Some laboratories might charge patients for CD4 testing. If the patient does not have health insurance or ability to pay for CD4 testing, individual patients might not receive CD4 testing (and then would not receive CrAg testing).

Such sources of instability will be monitored as factors related to feasibility of CrAg screening.

## 6. Sample size calculation:

The two primary outcomes of the study are 1) the estimate of the percentage of prescreened patients who have  $CD4 \leq 100$  cells/ $\mu L$  and 2) Of those with  $CD4 \leq 100$  cells/ $\mu L$ , the estimate of the percentage who are CrAg+. For these primary outcomes, data will come from both Phase 1 and Phase 2. From study initiation to October 31 2016 (approximately 13 months), we prescreened 2,612 participants, and 1068 of these had a  $CD4 \leq 100$  cells/ $\mu L$ . Of those, 957 enrolled, and 25(2.6%) were CrAg+. Assuming a similar enrollment rate (74 per month), upon the completion of Phase 1 (March 2017), we will have prescreened 3,014 participants and would expect 1,232 to have  $CD4 \leq 100$  cells/ $\mu L$  and 1,104 to be enrolled in the follow up study. Of these, we would expect approximately 29 to be CrAg+.

For Phase 2 (presumably from February 2017 to September 2017), plan to prescreen an additional 1,808 patients. Taking both data from Phase 1 and Phase 2 into account, we would expect to prescreen 4,822 patients and to document 1,972 patients with  $CD4 \leq 100$  cells/ $\mu L$ . In total, we would expect approximately 46 patients to be CrAg+.

Table 3 presents confidence limits for the two primary outcomes based on these assumptions and incorporating a design effect (DEFF) to account for the within-facility clustering of observations. The design effect is computed as  $[1+(m-1) \text{ ICC}]$  where  $m$  is the average number of patients per facility and ICC is the intraclass correlation coefficient. There is no local data on which to base assumptions about the magnitude of the within-clinic correlation in Vietnam, but a recent publication reports intraclass correlation coefficients (ICCs) of about .02 or smaller for health-related variables in an HIV-positive clinic population in sub-Saharan Africa [4]. Taking data from Phase 1 into account only, for the first primary outcome,  $m$  is 137 (3014/22) and for the second primary outcome,  $m$  is 56 (1,232/22). Taking data from both Phase 1 and Phase 2 into account,  $m$  is 219 (4822/22) and is 90 (1972/22) for the first and the second primary outcomes respectively.

**Table 3. Precision for primary study outcomes based on projected enrollment in Phase 1 (through March 2017) and Phase 1 + Phase 2 (projected through September 2017)**

Pre-screened	% with CD4≤100	Design Effect	95% confidence limits	Number tested for CrAg	% CrAg-positive	Number CrAg+	Design Effect	95% confidence limits
Phase 1 (projected through Dec 31, 2016)								
3,014	40.9	3.72	37.5, 44.3	1,232	2.6	29	2.10	1.30, 3.90
Phase 1 + Phase 2 (projected through September 2017 among 22 study OPCs only)								
4,822	40.9	5.36	37.7, 44.1	1,972	2.6	46	2.78	1.40, 3.80

Note: Confidence limits are inflated by a design effect of  $[1+(m-1) \rho]$  where m is the average number of patients per facility and  $\rho$  is the intraclass correlation coefficient.

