**Objectives:**

**Primary objectives:**

- To estimate the proportion of people living with HIV (PLHIV) who have advanced disease ( $CD4 \leq 100$  cells/ $\mu L$ ) at presentation to HIV care;
- To determine the prevalence of CrAg-positivity among HIV infected patients with  $CD4 \leq 100$  cells/ $\mu L$  newly enrolled in care in Vietnam;
- To determine clinical outcomes including common causes of mortality for PLHIV with  $CD4 \leq 100$  cells/ $\mu L$  who are enrolled in a programmatic rollout of screening for CrAg;
- To estimate the 12-month mortality among two groups of HIV-infected patients with  $CD4 \leq 100$  cells/ $\mu L$  who are newly enrolled in care and treatment:
  - Those who are CrAg-positive and are treated with high-dose fluconazole
  - Those who are CrAg-negative

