### **7.1.2. CrAg screening in Phase 2**

In Phase 2, CrAg screening will be performed as a routine service, and physicians will not prescreen patients according to study eligibility criteria. Rather, all routine laboratory requisition forms from the participants sites will be pre-marked with a note to the laboratory to perform reflex CrAg screening on any specimen with a  $CD4 \leq 100 \text{ cells}/\mu\text{L}$ . Providers will have a checkbox to mark the indication for the CD4 test on the requisition form, i.e., whether the CD4 test is being ordered for (1) new enrollment; (2) routine monitoring; or (3) presumed treatment failure. Laboratories will use the LFA provided by the study to perform reflexive CrAg screening with study LFA on specimens from patients with  $CD4 \leq 100 \text{ cells}/\mu\text{L}$  or signs/symptoms of meningitis or among outpatient or hospitalized patients with WHO stage 3 or 4 diseases at the discretion of the provider.

Results of the CD4 and CrAg tests will be recorded daily by the participating laboratories, and results sent to the requesting OPC or hospital along with the CD4 count. All laboratories participating in Phase 2 will record the CD4 count, CrAg result, and indication for CrAg test along with the code for the requesting site and other data that are routinely included on the requisition form (typically age and birth year). Because Phase 2 is being implemented programmatically, laboratories will have the choice whether to incorporate the CRICS data (e.g., CrAg result and indication for CD4) in their routine laboratory logs or to use logs provided by CRICS. The data will be collected by the project team on a regular basis.

Under Phase 2, participating CRICS laboratories are expected to inform the corresponding OPCs or inpatients wards, as well as the project team, of any CrAg-positive results as soon as possible. The patient's primary providers are responsible for prescription of fluconazole and follow up according to their standard care procedures and national

guidelines. Fluconazole supply for identified CrAg-positive patients will be provided by the study if not readily available for the patient at the participating sites. We will monitor the prevalence of CrAg positivity through labs without enrolling patients into the study.

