### **8.4 Monitoring visits**

#### a. Phase 1

Every 1-2months, the study coordinators/research associates/research assistant/data manager or other study staff will visit each of all study sites to supervise the study and collect data. Every six months, the regular visit will also includePrincipal Investigators or lead-coordinators and refresher training will be included as needed. The monitoring tasks include:

- Checking that patients with  $CD4 \leq 100$  cells/ $\mu L$  have all been screened for CrAg
- Checking the number of newly-enrolled patients
- Checking if all patients enrolled since the last clinical research associate (CRA) visit have signed the informed consent forms.
- Checking that fluconazole dosage of CrAg-positive patients is being changed according to protocol (section 7.4)
- Checking that all CRFs are properly filled.
- Checking the number of newly enrolled patients.
- Recording all emerging issues during implementation, including ascertainment of changes to routine CD4 or viral load testing due to financing or other reasons.

b. Phase 2 labs will be the focal point of contact in Phase 2 as all study activity related to CrAg screening and data collection will take place at labs. Thus, lab monitoring visits will be conducted on a monthly basis. The purpose of such monitoring visits is to:

- The number of CD4 tests performed and number of tests having CD4 count  $\leq 100$  cells/ $\mu L$
- The number of patients tested for CrAg and those with positive CrAg results
- Obtain an updated lists of OPCs and sites that are served by the lab
- The availability of reagents, the functioning of CD4 testing machines, and any factors that might influence the lab's ability to perform CD4 testing

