# **11. Data Analysis**

## **Data analysis plan:**

### **Primary objectives:**

Proportions will be calculated and presented with associated 95% confidence interval (CI). Clustering effect will be taken into account when calculating 95% CI.

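### Primary outcome 1 is drawn partly from Phase 2 CD4 tests with no restriction to patients newly entering care

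*Protocol*

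**What the plan says.** The Protocol Summary and Table 1 both set objective 1 as the proportion with CD4 ≤100 "at presentation to HIV care". The outcome measure beside it in Table 1 refers simply to HIV-infected adults and does not repeat the timing.

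Section 6 defines outcome 1 as the percentage of prescreened patients with CD4 ≤100. It says of both primary outcomes that "For these primary outcomes, data will come from both Phase 1 and Phase 2". For Phase 2 the team will "plan to prescreen an additional 1,808 patients", which brings the total to 4,822. The pooled row of Table 3 is limited to the 22 study OPCs (outpatient clinics). That is its only restriction.

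Section 7.1.2 describes Phase 2 differently: "physicians will not prescreen patients according to study eligibility criteria". The requisition form carries a checkbox for why the CD4 test was ordered: ("1) new enrollment; (2) routine monitoring; or (3) presumed treatment failure". Sections 3 and 4 confirm that treatment-experienced patients are covered in Phase 2.

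Among the items for Phase 2 laboratory monitoring visits, Section 8.4 lists "The number of CD4 tests performed and number of tests having CD4 count" at or below 100. The unit is tests, and no indication is named. For the primary objectives, Section 11 gives only proportions with cluster-adjusted 95% confidence intervals.

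**The concern.** Objective 1 describes people entering care. In Phase 1 the prescreening step selected roughly that group. Section 6 uses the same word for Phase 2, where the step does not exist. The nearest denominator that Phase 2 offers is the count of CD4 tests, and that count includes people already in care who are being monitored or investigated for treatment failure. Someone who follows Sections 6, 8.4 and 11 as written would put these tests into a primary estimate.

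The result would then depend partly on how many monitoring and failure tests the laboratories ran in 2017. The confidence interval would not show this, because it reflects sampling and clustering only. Part of the problem lies in data collection. If the tally for CD4 counts above 100 is taken without the indication, no later analysis rule can separate the groups, and those counts make up about 59% of the projected denominator (100 − 40.9).

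**Working it through.** **Inputs.** From Section 6 and Table 3: 1,068 of 2,612 prescreened patients had CD4 ≤100 over about 13 months (40.9%); projected n is 3,014 for Phase 1 and 4,822 for both phases; 22 clinics; intraclass correlation 0.02.

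**1. Table 3 reproduced.** DEFF = 1 + (m − 1) × 0.02; limits = p ± 1.96 × √(DEFF × p(1 − p)/n), with p = 0.409.

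- Phase 1: m = 3,014/22 = 137, DEFF = 3.72, half-width 3.39 points, limits 37.5–44.3, as stated.
- Both phases: m = 4,822/22 = 219, DEFF = 5.36, half-width 3.21 points, limits 37.7–44.1, as stated.

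The arithmetic is right. Pooling narrows the half-width by 3.39 − 3.21 = 0.18 points.

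**2. Where the 1,808 comes from.** 2,612/13 = 200.9 per month, and 200.9 × 9 = 1,808. The expected number with CD4 ≤100 in Phase 2 is 1,972 − 1,232 = 740, and 740/1,808 = 40.9%. The projection therefore carries forward the Phase 1 flow of new presenters at the Phase 1 proportion. The Phase 2 procedures do not select that population.

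**3. Effect if non-presentation tests fall within the 1,808.** Let f be their share and q the proportion of them with CD4 ≤100. The Protocol gives neither, so both are assumptions.

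Pooled = [3,014 × 0.409 + 1,808 × ((1 − f) × 0.409 + f × q)] / 4,822

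| f | q = 10% | q = 20% | q = 30% | q = 50% |
|---|---|---|---|---|
| 25% | 38.0% | 38.9% | 39.9% | 41.8% |
| 50% | 35.1% | 37.0% | 38.9% | 42.6% |
| 75% | 32.2% | 35.0% | 37.8% | 43.5% |

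Against 40.9%, the shift is downward when q is below 40.9% and upward when it is above.

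**4. Effect if such tests come on top of the 4,822.** With M extra tests, pooled = (4,822 × 0.409 + M × q)/(4,822 + M). For M = 300 this gives 39.1%, 39.7% or 40.3% at q = 10%, 20% or 30%. Reaching the planned lower limit of 37.7% takes M = 557, 872 or 2,004. As M/(1,808 + M), that is 24%, 33% or 53% of Phase 2 CD4 tests at these clinics.

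**5. Precision if Phase 2 is limited to new enrollments.** n = 3,014 + 1,808 × (1 − f), with DEFF recalculated from m = n/22.

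| Share of the 1,808 removed | n | DEFF | 95% limits |
|---|---|---|---|
| 0% | 4,822 | 5.36 | 37.7–44.1 |
| 25% | 4,370 | 4.95 | 37.7–44.1 |
| 50% | 3,918 | 4.54 | 37.6–44.2 |
| 75% | 3,466 | 4.13 | 37.6–44.2 |
| 100% (Phase 1 only) | 3,014 | 3.72 | 37.5–44.3 |

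**The case against.** The best defence is that the restriction already stands in the objective. Phase 2 does contain new enrollments, and Section 6 never says that every CD4 test is pooled. The choice of records could be left to an analysis plan. There are signs that new presenters were meant: the 1,808 is the Phase 1 rate carried forward, Section 10 codes the indication as baseline or follow-up, and Section 13.2 justifies laboratory abstraction by reference to baseline CD4. The needed variable also exists. The checkbox is on the requisition form, so it is completed before the CD4 result is known, and Sections 7.1.2, 7.3, 7.4, 10 and 10.1 all name the CD4 indication. Where Section 7.1.2 has laboratories record the "indication for CrAg test along with the code for the requesting site", this looks like a slip, since the next lines refer to the indication for CD4.

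Much of this stands. A reader might infer that the indication is not collected at all, and the text does not support that. What remains open is narrower: the abstraction passages describe patients screened for cryptococcal antigen, and the tally in Section 8.4 omits the indication, so coverage of CD4 counts above 100 is not explicit.

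The size of the effect is also uncertain. Sections 1.2 and 5 report that CD4 testing is being scaled down, which could keep the admixture small, and 300 extra tests would leave the estimate inside the planned interval.

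The defence fails on one point. Section 6 names a Phase 2 denominator that Section 7.1.2 says will not exist. That is a conflict within the Protocol, not a detail it has left open.

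**Conclusion.** The point holds and should be fixed. Sections 6, 8.4 and 11, followed as written, mix patients already in care into an estimate meant for people presenting to care.

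The size is conditional. With half of the 1,808 being such tests and 10% to 30% of them at CD4 ≤100, the pooled figure is 35.1% to 38.9%; at 50% it is 42.6%. These shares are assumptions.

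Two stronger readings are not supported. One is that outcome 1 will be biased downward by a known amount: the Protocol gives no test mix, and the direction can reverse. The other is that the prevalence of cryptococcal antigen is compromised in the same way. There the Protocol Summary speaks of newly enrolled patients and the Table 1 outcome measure of all adults with CD4 ≤100, which is a difference of wording. Suppose 25% or 50% of the 740 Phase 2 patients were not new and had a prevalence of 1.3% or 5.2%, that is, half or twice the planned 2.6%. The result is then 2.4% to 3.1%, inside the planned 1.4–3.8.

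**What to change.** - In Sections 6 and 11, limit the Phase 2 contribution to outcome 1 to CD4 tests marked as new enrollment at the 22 study OPCs, counted once per patient as far as the data allow.
- In Section 6, drop the prescreening term for Phase 2, and state that the 1,808 refers to such patients or revise it.
- In Section 8.4, have the laboratory tally split both the CD4 tests and the results at or below 100 by the indication already on the requisition form, so that counts above 100 are covered.
- If the indication cannot be obtained for counts above 100, use Phase 1 alone for outcome 1.

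The cost is a few sentences and slightly more tallying. Split counts are still aggregate data, so they fit the waiver described in Section 13.2, and no identifier for every CD4 test is needed. The interval would be no wider than about 37.5–44.3, against 37.7–44.1. Two limits remain. Repeat tests cannot be fully removed where no patient identifier is held. The new-enrollment box also does not reproduce the Phase 1 eligibility criteria, so the two phases will be closer but not identical in population.

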## 7. Study procedures

### 7.1. CrAg Screening Implementation (Reflex testing, return of results, communicating results and enrolment into the prospective cohort)

#### 7.1.1. CrAg screening in study OPCs in Phase 1

As CrAg screening is a WHO and Vietnam MOH national recommendation, it is considered SOC for persons with advanced HIV (CD4≤100 cells/ $\mu$ L), and reflexive testing does not require informed consent. All adult patients presenting for ART evaluation and who provide a sample for CD4 testing will be educated about the risks of OIs such as CM and tested for cryptococcal antigen in accordance with national guidance. They will be specifically informed about CrAg screening prior to their blood draw using a short script (See Appendix 1: Screening , Appendix 2A: Script informing patients of CrAg screening (English)and Appendix).

Patients will be told that those with low CD4 whose CrAg results are positive will be contacted by the clinic to invite them back for an earlier appointment. Results of the CD4 and CrAg tests will be sent to the respective clinics within 24 hours of the tests, and made available to physicians (Appendix 15: CrAg Testing Request Form). Results of the CD4 and CrAg tests will be recorded daily into the evaluation logs at the participating laboratories and respective clinics (see Appendix and Appendix 16: CrAg testing log for the lab).

Once the clinic receives the test results, OPC staff will be responsible for contacting the patients who are CrAg-positive by telephone with the results within 24 hour sand request

them to return to the clinic for an earlier appointment. Three attempts will be made to reach the patient by phone or Short Message Service (SMS) and if not reachable, the patient will be seen at his routine scheduled appointment which is normally within two weeks of the date of CD4 testing. When patients with  $CD4 \leq 100 \text{ cells}/\mu\text{L}$  return to the clinic, they will be informed of the results of both the CD4 and plasma CrAg testing. Procedures for the prospective cohort evaluation and data collection will be described. If the patient agrees to participate, s/he will sign the consent form for enrollment (see Appendix 3A: Inform Consent Form (English)) and will be assigned a study identification (ID) number. This will be considered a study visit since in routine practice, patients only return for their CD4 at the next scheduled visit, usually 1-2 weeks after that date of sample collection.

### **7.1.2. CrAg screening in Phase 2**

In Phase 2, CrAg screening will be performed as a routine service, and physicians will not prescreen patients according to study eligibility criteria. Rather, all routine laboratory requisition forms from the participants sites will be pre-marked with a note to the laboratory to perform reflex CrAg screening on any specimen with a  $CD4 \leq 100 \text{ cells}/\mu\text{L}$ . Providers will have a checkbox to mark the indication for the CD4 test on the requisition form, i.e., whether the CD4 test is being ordered for (1) new enrollment; (2) routine monitoring; or (3) presumed treatment failure. Laboratories will use the LFA provided by the study to perform reflexive CrAg screening with study LFA on specimens from patients with  $CD4 \leq 100 \text{ cells}/\mu\text{L}$  or signs/symptoms of meningitis or among outpatient or hospitalized patients with WHO stage 3 or 4 diseases at the discretion of the provider.

Results of the CD4 and CrAg tests will be recorded daily by the participating laboratories, and results sent to the requesting OPC or hospital along with the CD4 count. All laboratories participating in Phase 2 will record the CD4 count, CrAg result, and indication for CrAg test along with the code for the requesting site and other data that are routinely included on the requisition form (typically age and birth year). Because Phase 2 is being implemented programmatically, laboratories will have the choice whether to incorporate the CRICS data (e.g., CrAg result and indication for CD4) in their routine laboratory logs or to use logs provided by CRICS. The data will be collected by the project team on a regular basis.

Under Phase 2, participating CRICS laboratories are expected to inform the corresponding OPCs or inpatients wards, as well as the project team, of any CrAg-positive results as soon as possible. The patient's primary providers are responsible for prescription of fluconazole and follow up according to their standard care procedures and national

guidelines. Fluconazole supply for identified CrAg-positive patients will be provided by the study if not readily available for the patient at the participating sites. We will monitor the prevalence of CrAg positivity through labs without enrolling patients into the study.

